In preparation for the interim analysis, all available serum specimens from the PK cohort will be shipped for MPA testing at PPD approximately 8-10 weeks prior to the scheduled interim DSMB meeting. Once MPA results are received at FHI 360, baseline specimens will be analyzed to inform the following decision. If more than 10% of tested baseline specimens from the PK cohort have MPA concentrations greater than or equal to 0.1 ng/mL, or if more than 20% of tested baseline specimens from the PK cohort have MPA concentrations greater than or equal to 0.05 ng/mL, then the study team will proceed with MPA testing of all baseline specimens from the main cohort.

As soon as the decision is made to test baseline specimens from the main cohort (if applicable), all available baseline specimens from participants in the main cohort will be shipped to PPD for MPA testing. Once serum MPA results from this enrolled subset of the main cohort are received at FHI 360, baseline specimens will be analyzed to inform the following second decision. If more than 10% of tested baseline specimens from the main cohort have MPA concentrations greater than or equal to 0.1 ng/mL, or if more than 20% of tested baseline specimens from the main cohort have MPA concentrations greater than or equal to 0.05 ng/mL, then the study team will make a determination as to whether subjects with baseline levels exceeding a threshold should be excluded from the primary analysis, and initiate a discussion with the study funder surrounding the potential for expansion of enrollment to account for such exclusions.

Specimens from the remainder of the main study cohort (enrolled after the first batch are shipped) will be sent to PPD for testing at a later time in order to inform any analysis decisions. Any analysis decisions made based on results of MPA testing of baseline specimens from main cohort participants will be made blind to pregnancy outcome results and will be recorded in future versions of the analysis plan or in the final report as appropriate.

XVI. Appendices

A. Visit Windows for MPA Measurements (PK Cohort Only)

Visit	Target Day (Window)	In-Window Range (inclusive)
Month 2	61 (+/-7)	54-68
Month 3	91 (+/-7)	84-98
Month 4	119 (+7)	119-126
Month 8*	245 (+7)	245-252
Month 12*	371 (+7)	371-378

*The target days for these visits will be shifted if a participant is more than 7 days (but less than 29 days) late for reinjection at the previous visit. If so, the target day(s) for the remaining visit(s) will be calculated in 126-day intervals after date of delayed reinjection (with the corresponding 7-day window). For example, if a participant comes in for her Month 4 visit on day 130, then her Month 8 target day (in-window range) becomes 256 (256-263) and her Month 12 target day (in-window range) becomes 382 (382-389).

B. Changes to the Analysis Plan after Approval of Version 1.0

i. Changes implemented in SAP version 2.0

- Updated randomization section to reference re-allocation of 100 participants to DR from Brazil due to slow recruitment at Brazil
- Added footnote clarifying how protocol violations at enrollment will be addressed within the primary efficacy analysis in section IX.B
- Added sensitivity analysis to assess efficacy after excluding women with protocol violations surrounding enrollment
- Added criteria for testing baseline specimens of MPA in the main study cohort based on results of baseline testing in the PK cohort
- Added possible exploratory analysis to look at intra-subject variability in trough levels across injection cycles

ii. Changes implemented in SAP version 3.0

- Added exploratory objective and endpoint per version 8.0-B of the protocol; added statement that analysis of this objective will be described separately
- Revised baseline and disposition tables to change summaries by injection site within study center to simply by study center
- Revised definition of PK Population and Analysis Set to exclude any time after relevant injections for participants whose provider was required to use more than one device to deliver the drug
- Moved previously defined sensitivity analysis in section IX.B to new section specifically for sensitivity analyses (XII)
- Defined one new sensitivity analysis for the efficacy objective around home pregnancy tests
- Defined two sensitivity analyses for the PK objective, based on baseline MPA concentrations and injection issues

Certificate Of Completion

Envelope Id: 10BA9DC99611454C968930D2930880CA

Status: Completed

Subject: Please DocuSign: Study 926400 Statistical Analysis Plan v3.0 (28MAY2020)-Clean.pdf

CF02:

Project Code/Charge Code: 102137.002.001.001.003

Source Envelope:

Document Pages: 18

Signatures: 3

Envelope Originator:

Certificate Pages: 5

Initials: 0

[name]

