Baseline data will be presented for the Treated and PK Analysis Populations by injection site, study center, and pooled across injection sites and study center. Demographic and baseline characteristics, including medical history and concomitant medication use, will be provided in participant-specific listings and summarized using appropriate measures (frequencies and percentages for categorical data; means, standard deviations, standard errors, medians, minima, and maxima for continuous data). Differences in distributions of these characteristics

³ At the time of injection, some Uniject devices were discovered to have malfunctioned after the needle had already been inserted into the participant's skin. In these cases, a second device was used. Because we cannot guarantee that no product was injected from the first device, we chose to exclude affected results.

between study centers will be assessed using exploratory analysis of variance for continuous variables and Fisher's Exact tests for categorical variables.

VIII. Analysis of Participant Disposition Data

Participant disposition data will be presented for the Treated and PK Analysis Populations, by injection site, study center, and pooled across injection sites and study centers. The numbers of participants screened, screened but not enrolled (including reason(s) not enrolled), randomized, treated (including reason(s) not treated, if any), and final status (e.g., early withdrawal (and reason), completed the study, etc.) will be summarized using frequencies and percentages. A diagram showing the flow of participants through the trial will be provided, as will a listing including study center, inclusion in the PK cohort, randomized injection site, actual injection site, final study status, and any other information that the study team determines to be relevant. Protocol violations will be provided in a listing and may also be summarized in a table using frequencies and percentages of violations falling into each of the categories given by the deviation code on the protocol violation form. The "other" violation category may be divided into additional categories if consistent themes appear.

IX. Analysis of Primary Study Objective

A. Primary Objective and Endpoint

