The primary study objective is to evaluate the effectiveness of Sayana® Press when injected subcutaneously every 4 months in the abdomen or upper thigh for 12 months (3 treatment cycles) of use. The primary endpoint is the occurrence of pregnancy, as defined by a positive urine pregnancy test. Positive urine tests will be confirmed by ultrasound and/or serum hCG testing whenever possible. The EDF for each pregnancy will be calculated by a qualified study clinician based on ultrasound and last menstrual period (LMP) in accordance with the study Medical Monitoring Plan. In the absence of ultrasound or LMP, best clinical judgment will be used to estimate the EDF based on all available related information including but not limited to vaginal bleeding, patterns of coitus, and the timing of previous negative pregnancy test results.

Information on any pregnancies, miscarriages or abortions diagnosed outside the study center will be collected during follow-up interviews. Any such pregnancies with EDF determined to be within the treatment period will be included in the primary efficacy analysis unless the site investigator and study clinician unambiguously determine that the pregnancy diagnosis was incorrect and/or the self-reported data was unreliable.

B. Primary Efficacy Analysis

The primary efficacy analysis will be performed using the Treated Population⁴ and the Treated Analysis Set. Recognizing the plus 7-day grace period for re-injections, pregnancies with an EDF

⁴ Exclusion of participants from the primary efficacy analysis based on protocol violations occurring at enrollment (such as participant being enrolled while ineligible) will be considered on a case-by-case basis. A decision regarding inclusion of the participant will be made by the principle investigator in consult with the medical monitor and lead biostatistician. If possible, the decision will be made while these staff remain blinded to injection site and before

up to 18 weeks (126 days) after the first (enrollment) injection or up to 19 weeks (133 days) after subsequent re-injections will be included in the primary efficacy analysis.

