The primary analysis of efficacy will be based on the pregnancy Pearl Index, defined as the number of pregnancies that occur during the treatment period per 100 women-years of time contributed to the Treated Analysis Set among women randomized to receive injections in the abdomen or thigh. Participants who do not become pregnant or who have EDFs that fall outside the windows used to define primary outcomes will be censored on the date of last negative urine pregnancy test or the end of the plus 7-day grace period since last injection, whichever is earlier. An exact 95% confidence interval for the Pearl Index will be computed based on an assumption that the number of pregnancies occurring in the treatment period follows a Poisson distribution. A listing of all participants who become pregnant during the study will include at least study center, randomized injection site, days on treatment until EDF, inclusion in the primary efficacy analysis, and pregnancy outcome.

C. Secondary Efficacy Analysis

Secondary efficacy analyses will include:

- Typical use life-table estimates of the cumulative probability of pregnancy through 3 treatment cycles, based on the Treated Population and Safety Analysis Set (excluding women randomized to receive injections in the upper arm). Point-wise 95% confidence intervals will be computed using the log-log transformation. For this analysis, the first, second and third treatment cycle can be up to 21, 22, and 22 weeks long, respectively (after accounting for up to a 28-day late period for re-injections or final study visit).
- An estimate of the Pearl Index computed based on the Perfect Use Analysis Set (excluding participants randomized to receive injections in the upper arm).
- An estimate of the Pearl Index based on the Treated Population and Safety Analysis Set (excluding participants randomized to receive injections in the upper arm). This estimate will include all follow-up time contributed (regardless of pregnancy status) and any pregnancies detected while participants are up to 28 days late for their visits.
- An estimate of the Pearl Index computed per the primary analysis, but including women randomized to receive injections in the upper arm.

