In addition to the non-comparative analyses listed above, a Pearl Index based on the Treated Analysis Set will be computed separately for participants randomized to receive injections in the abdomen, thigh, and upper arm. Difference in pregnancy risk between groups will be assessed using a log-rank test stratified on study center. If pregnancy events are sufficiently rare so as to make this test inappropriate, this difference will be assessed using 95% confidence intervals for incident rate ratios based on Poisson distribution assumptions instead. If at least 5 pregnancies occur in one or more of the injection site groups, then the cumulative risk of pregnancy in each group will also be estimated using life-tables methods.

results of any pregnancy tests are known for the participant in question. The actual level of blinding when decisions are made will be documented in future versions of the analysis plan or in the final report as appropriate.

X. Analysis of Secondary Study Objectives

The secondary study objectives are to assess the following when Sayana® Press is injected every 4 months for 12 months of use: 1) trough concentrations, accumulation, and apparent terminal half-life of MPA, and the impact of subcutaneous injection site (abdomen, upper thigh, or back of the upper arm) on these parameters, 2) the safety of Sayana® Press, and 3) the acceptability of Sayana® Press.

A. Pharmacokinetics of MPA

PK endpoints include serum MPA concentrations at baseline and months 2, 3, 4, 8, and 12. Post-baseline MPA concentrations that fall below the limit of quantification (LOQ) will be replaced by half the applicable LOQ. PK analyses will be performed using the PK Analysis Population and Set.

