Two sensitivity analyses will be performed for the efficacy objective. A Pearl Index and exact 95% confidence interval will be computed per the primary analysis (section IX.B) but excluding any women who had protocol violations occurring at enrollment that warrant exclusion based on blind review. Another Pearl Index and exact 95% confidence interval will be computed per the primary analysis but excluding results from pregnancy tests taken at home and any time between a participant's last in-clinic pregnancy test and her exit from the study. This will assess the impact of final pregnancy tests completed at home in response to the COVID-19 pandemic.

Two sensitivity analyses will be performed for the PK objective. The first will assess the impact of baseline MPA on PK profiles and will include all participants (except for those who required the use of more than one Sayana Press unit) in the PK cohort who provide samples for MPA testing. This will be done in the following way: calculate the half-life (λ) for each injection site using the same method described in the secondary objective above but using the revised population; use that half-life to calculate the concentration at time t (CB_t) due to the baseline amount (C_0) using the following formula

$$CB_t = C_0 e^{-\lambda t};$$

then subtract that amount from the corresponding monthly concentrations for each participant. Summaries of trough concentrations will be provided using these modified values and population.

Secondly, a table summarizing trough concentrations and half-life will be provided for a population comprised of the PK Population plus any participants or samples excluded from the PK Population or Analysis Set based on injection issues (i.e., more than one unit inserted into skin).

XIV. Planned Interim Analyses

An independent DSMB will review interim data when approximately 250 participants have completed 18 weeks of follow-up. This single, pre-planned interim analysis is intended to inform a decision whether to stop or modify the study if the estimated probability of pregnancy pooled across all injection sites is greater than 2% in the first injection interval. Details are provided in a separate DSMB Operational Plan.

XV. MPA Testing of Baseline Serum Specimens

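### SAP footnote 4 allows enrollment violators to be dropped from the primary Pearl Index without mandatory blinding to pregnancy results, and when used it overlaps with the SAP XIII sensitivity analysis

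*SAP*

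**What the plan says.** SAP IX.B runs the primary analysis on the Treated Population. SAP V.A and Protocol 10.2.1 both define this as enrolled women who received a dose, with no removal for ineligibility.

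Footnote 4 to SAP IX.B adds the exception. It concerns "Exclusion of participants from the primary efficacy analysis based on protocol violations occurring at enrollment", and cases "such as participant being enrolled while ineligible) will be considered on a case-by-case basis". The principal investigator decides with the medical monitor and the lead biostatistician. On blinding it says: "If possible, the decision will be made while these staff remain blinded to injection site and before" (continuing) "results of any pregnancy tests are known for the participant in question". It then adds: "The actual level of blinding when decisions are made will be documented in future versions of the analysis plan or in the final report". Apart from the one example, it does not say which violations qualify.

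Three other places bear on this:

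- **SAP XIII** plans a Pearl Index computed as in the primary analysis, "but excluding any women who had protocol violations occurring at enrollment that warrant exclusion based on blind review".
- **SAP VI** describes blind review in terms of access to individual treatment data, as far as possible. It does not mention pregnancy outcome.
- **SAP XV** may lead to exclusions from the primary for high baseline MPA. It requires those decisions to be blind to pregnancy outcome, with no qualifier.

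On disclosure, SAP VIII states that "Protocol violations will be provided in a listing", and the listing of pregnancies in SAP IX.B is to show "inclusion in the primary efficacy analysis, and pregnancy outcome".

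**The concern.** The primary result is a single rate built on a handful of pregnancies. A rule that lets a woman be removed after her pregnancy result is known allows the numerator to depend on a discretionary, outcome-aware decision. The situation is realistic: every woman is due a urine pregnancy test at month 4, so an eligibility breach found after that visit may be judged with her result already on file. This is an inference about timing, but it is the case that the qualifier in footnote 4 leaves open.

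The second problem is the overlap with SAP XIII. If women have already been removed under footnote 4, a sensitivity analysis defined as the primary minus such women removes them again. To the extent that the two sets coincide, it returns the primary result and cannot show the effect of the exclusions. Neither passage says which women belong to which analysis.

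**Working it through.** **Inputs.** From the documents: 710 women in the primary population; at least 80% completing 12 months; a precision target of upper 95% bound minus index of at most 1.0 when the observed index is below 0.75; a true rate of 0.5 per 100 woman-years (WY) (all SAP III.A); and exact Poisson 95% limits (SAP IX.B). The documents do not state total WY, so these are assumptions:

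- low: 710 × 0.80 × 1 year = 568 WY (dropouts contribute nothing);
- working value: 568 + 142 × 0.5 = 639 WY (dropouts contribute half a year on average);
- high: 710 × 54 × 7 / 365.25 = 735 WY (every woman contributes the 54 weeks of the example in SAP V.A).

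**Formula.** Index = 100x/WY. Upper bound = 100 × U(x)/WY, where U(x) is half the 97.5% point of chi-square with 2x + 2 degrees of freedom. U(3) = 8.767 and U(4) = 10.242.

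**The plan's own figure.** At 639 WY the largest count with an index below 0.75 is 4 (5 gives 0.782). For x = 4 the index is 0.626, the upper bound 1.603 and the difference 0.977. The target of 1.0 is reproduced. At 568 WY it is not (1.803 − 0.704 = 1.099).

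**Expected events at 0.5 per 100 WY.** 2.84, 3.20 and 3.68 pregnancies at 568, 639 and 735 WY.

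**One pregnant woman excluded, 4 to 3 events.**

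| Assumed WY | Index (upper bound), 4 events | Index (upper bound), 3 events |
|---|---|---|
| 568 | 0.704 (1.803) | 0.528 (1.544) |
| 639 | 0.626 (1.603) | 0.469 (1.372) |
| 735 | 0.544 (1.393) | 0.408 (1.193) |

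The relative fall in the index is 1/4 = 25% from 4 events and 1/3 = 33% from 3. Removing her own time as well (assumed 0.5 WY) changes little: 3/638.5 gives 0.470.

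**Non-pregnant women excluded.** Five women with 1 WY each at 639 WY: 4/634 gives 0.631 against 0.626, a rise of 0.005. With 3 events, 3/634 gives 0.473 against 0.469. To raise the index by as much as one excluded pregnancy lowers it, solve 4/(639 − n) = 5/639, so n = 127.8, or about 128 women.

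**Effect on the precision target.** From 4 to 3 events, bound minus index goes from 1.099 to 1.016 at 568 WY (missed both times), from 0.977 to 0.903 at 639 WY (met both times) and from 0.849 to 0.785 at 735 WY (met both times). At 639 WY the status changes if 5 events become 4: 1.044 to 0.977.

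**Footnote 4 against SAP XIII.**

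- No woman removed under footnote 4: SAP XIII works as written.
- Some removed, and SAP XIII removes the same women: the two results are identical.
- Some removed, and SAP XIII removes others as well: SAP XIII shows only the effect of the others.

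In the second and third cases, SAP XIII does not show the effect of the footnote 4 exclusions.

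**The case against.** **The two passages can coexist.** Footnote 4 says only that exclusion will be considered. The default is the full Treated Population, and the SAP change log shows that both provisions were added in version 2.0. A reader might infer an outright contradiction; the text does not support that. They overlap only if footnote 4 is used, and what is needed is reconciliation.

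**An index that restores the women is already planned.** The third secondary analysis in SAP IX.C is a pooled abdomen-plus-thigh Pearl Index on the Treated Population and Safety Analysis Set. Footnote 4 is confined to the primary, so this index appears to bring excluded women back. It would be wrong to say that no such analysis exists. But it also counts late time and late pregnancies, so a difference from the primary mixes two effects. The separate indices by injection site may also keep these women, but the SAP does not say so.

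**Footnote 4 gives no reason for departing from the protocol.** A reader might infer a breach of Protocol 10.13. That section also allows reasons to be given in the clinical study report, so no breach follows.

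**Blinding cannot always be achieved.** This stands in part. Not being pregnant is an inclusion criterion, and its breach may come to light only through a pregnancy result. It calls for a separate rule for that case and does not justify a general qualifier.

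**Disclosure is planned.** The two listings and the documented level of blinding would let a reader see an outcome-aware exclusion. They act afterwards and do not prevent it.

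**Excluding women who are not at risk is defensible.** That also stands, but for a few women the effect is small and SAP XIII can show it.

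**Conclusion.** The concern holds in this form: footnote 4 permits selection into the primary analysis that depends on the outcome, while SAP XV sets a firmer standard for a comparable decision. Using footnote 4 also makes SAP XIII wholly or partly redundant.

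The size is conditional on an excluded violator being pregnant. One such decision then lowers the index by a quarter to a third at the expected event counts (about 0.16 per 100 WY at the assumed 639 WY, or 0.14 to 0.18 over 568 to 735 WY). The documents give neither the WY nor the chance of this happening, and nothing in them suggests that such exclusions were made or intended. The trial has a precision target rather than an efficacy pass mark. Going from 4 to 3 events does not change whether that target is met at any of the three WY values. What is at stake is the credibility of the headline estimate and its upper bound. The text supports the point with high confidence, and the change should be made.

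**What to change.** **Preferred.** Keep all treated women randomized to abdomen or thigh in the primary Pearl Index. Apply enrollment-violation exclusions only in SAP XIII, list the violations that qualify, and require decisions to be blind to pregnancy outcome. Handle a pregnancy already present at enrollment through the estimated date of fertilization: state that a date before the first injection is not an on-treatment pregnancy, so no discretionary exclusion is needed.

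**Alternative.** If exclusions stay in the primary, require the same listed criteria and outcome blinding, and redefine the SAP XIII analysis as the all-treated Pearl Index under the primary's time rules, so that the effect of the exclusions can be read directly.

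**Cost.** SAP wording only. Under the preferred option a few ineligible women, possibly not at risk of pregnancy, stay in the denominator and lower the index slightly: about 0.005 for five women at 639 WY with 4 pregnancies. SAP XIII would show this.
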